### **Physical Examination and Laboratory Results**

- 18. Significant abnormal liver function results at screening, defined as alanine aminotransferase (ALT)> 2.5×upper limit of normal (ULN), or aspartate aminotransferase (AST)> 2.5×ULN or serum total bilirubin (TBiL)> 1.5×ULN (refer to Appendix 6).
- 19. Serological evidence of hepatitis virus infection at screening: positive hepatitis A virus IgM antibody (IgM anti-HAV), or positive hepatitis B surface antigen (HBsAg) and IgM antibody to hepatitis B core antigen (IgM anti-HBc) (to exclude subjects with acute hepatitis virus B infection), or positive hepatitis C virus antibody (anti-HCV).
- 20. Estimated glomerular filtration rate (eGFR)< 60 mL/min/1.73m^2 at screening.
- 21. Triglyceride> 5.7 mmol/L at screening.
- 22. Anemia of any causes, which is defined as: hemoglobin < 12.0 g/dL (120 g/L) for males and hemoglobin< 11.0 g/dL (110 g/L) for females at screening.

- 23. Abnormal laboratory results that may interfere with the safety evaluation, as judged by the Investigator.
- 24. Abnormal electrocardiogram (ECG) results that may affect the safety evaluation or need medical interventions, as judged by the Investigator (except for stable coronary heart disease).
- 25. Systolic blood pressure  $\geq$  160 mmHg or diastolic blood pressure  $\geq$  100 mmHg at screening or add/change antihypertensive drugs or adjust antihypertensive treatment doses within 4 weeks before screening.

### **Allergies and Adverse Drug Reactions**

- 26. Subjects who are potentially allergic or do not tolerate study medications, as considered by the Investigator.

### **Prohibited Therapies and/or Medications**

- 27. Subjects who refuse to only take the antidiabetic medications specified by the study protocol.
- 28. Current treatment with potent or moderate CYP3A4 inducers or inhibitors (see Section 4.4.2).

### **Sex and Reproductive Status**

- 29. Women who are pregnant or intend to be pregnant during the study.
- 30. Women in breastfeeding.
- 31. Women with childbearing potential and refuse to take high-efficient or clinically accredited contraceptive methods throughout the study and within 1 month after the last dose of study medications.

### **Other Exclusion Criteria**

- 1. Subjects who have any accompanied diseases or medical conditions that may interfere with them to complete the whole study or participate all procedures of the study on the basis of Investigator's judgment.
- 2. Subjects who need other therapy which may potentially affect the interpretation of efficacy and safety data of the study, as decided by the Investigator.
- 3. Subjects who are unable to comply with the study protocol, e.g., unable to keep persistent on dietary and exercise therapy during the study, to take medications and meals timely per study protocol, and to conduct SMBG and

[figure not shown]
	
make record timely.
 
4. Subjects who took any investigational drug or participated in any clinical study within 30 days before screening.
 
Randomization Criteria (laboratory tests and 12-lead ECG for qualification of randomization are conducted on Day -5 [<math>\pm</math> 2 days])
 
at Visit 4 (randomization visit), the following criteria will be re-evaluated to confirm eligibility before randomization. Subjects who meet the following randomization criteria are eligible to be randomized.
 
Inclusion Criteria
 
 
1. <math>\text{HbA1c} \geq 7.5\%</math> and <math>\leq 10.0\%</math> at pre-randomization visit.
 
2. Fasting blood glucose (FPG) <math>> 7.0</math> mmol/L and <math>< 13.3</math> mmol/L at pre-randomization visit.
 
 
Exclusion Criteria
 
 
3. History of severe hypoglycemia (requiring external assistance for recovery) or recurrent hypoglycemia (such as experience of 3 or more times of hypoglycemia <math>\leq 3.9</math> mmol/L or hypoglycemia symptoms within 1 month) without contributing factors within 3 months in run-in period.
 
4. Body weight change (weight gain or loss) <math>\geq 10\%</math> at randomization compared with that at screening.
 
5. Poor adherence to treatment in run-in period (<math>< 80\%</math> or <math>> 120\%</math>).
 
6. Significant abnormal liver function occurred in run-in period, defined as <math>\text{ALT} > 2.5 \times \text{ULN}</math>, or <math>\text{AST} > 2.5 \times \text{ULN}</math> or <math>\text{TBiL} > 1.5 \times \text{ULN}</math> at pre-randomization visit (refer to Appendix 6).
 
7. <math>\text{eGFR} < 60</math> mL/min/1.73m^2 at pre-randomization visit.
 
8. Triglycerides <math>> 5.7</math> mmol/L at pre-randomization visit.
 
9. Anemia of any causes, defined as hemoglobin <math>< 12.0</math> g/dL (120 g/L) for male, and hemoglobin <math>< 11.0</math> g/dL (110 g/L) for female at pre-randomization visit.
 
10. Systolic blood pressure <math>\geq 160</math> mmHg or diastolic blood pressure <math>\geq 100</math> mmHg at randomization visit or add/change medication or adjust doses of antihypertensive regimen in run-in period.
 
11. Abnormal laboratory results that may affect the safety evaluation of the study,
 

--	--

	
as judged by the Investigator.
 
12. Abnormal ECG results that may affect the safety evaluation of the study or need medical interventions, as judged by the Investigator (except for stable coronary heart disease).
 
13. The Investigator reconfirm the medical history and concurrent disease occurred before randomization (refer to the exclusion criteria at screening visit).

Study Hypothesis	
The HbA1c reduction after 24-week treatment with HMS5552 75 mg BID is significantly superior to that with placebo in subjects with T2DM.

Efficacy Endpoints	
Primary Efficacy Endpoint
 
To compare the change of HbA1c level from baseline in subjects with T2DM in the treatment group (HMS5552 tablets, 75 mg BID, oral) with the placebo group after 24-week double-blind treatment.
 
Secondary Efficacy Endpoints
 
To compare the treatment group (HMS5552 tablets, 75 mg BID, oral) with placebo group after 24-week double-blind treatment:
 
 
1. Change of 2-hour postprandial plasma glucose (2h-PPG) from baseline
 
2. Change of FPG from baseline
 
3. HbA1c response rate: the proportion of subjects whose HbA1c < 7.0%
 
4. Change of HbA1c from baseline at each visit, except Week 24.
 

Safety Endpoints	
 
• Adverse events (AEs) throughout the study
 
• Hypoglycemic events
 
• Physical examination
 
• Vital signs
 
• 12-lead ECG
 
• Clinical laboratory examinations (hematology, biochemistry and urinalysis)
 

Investigational Products	
Study drug HMS5552 tablets, strength 75 mg/tablet, BID, one tablet each time, prefer to take before meals
 
Control drug Placebo tablets, BID, one tablet each time, prefer to take before meals

Usage and Dosage of Study Medications	
Run-in period Control drug, continue to take for 4 weeks
 
Double-blind treatment period Study drug or control drug, continue to take for 24 weeks
 
Open-label treatment period Study drug, continue to take for 28 weeks
 
Safety follow-up period None

Statistical Considerations	
Sample size
 
 
1. This study plans to recruit 450 subjects. The subject number is possible to be increased by 20% if drop-out is considered. It is estimated that the total subject number is no more than 564. Subjects are randomized at a ratio of 2:1 to the treatment group (HMS5552) or the control group (placebo), i.e. no more than 376 subjects in the treatment group and 188 subjects in the control group.
 
2. Evaluation. Study results are analyzed based on the planned sample size and randomization ratio (450 subjects, treatment group: placebo group = 2:1). A type I error level of 0.05 (two-sided) is used and standard deviation within group for primary efficacy endpoint (change of HbA1c level from baseline) is assumed as 1.2%. If the difference between treatment and control groups (treatment group-control group) is -0.4%, it can be demonstrated with 91.4% power that the efficacy for treatment group is superior to control group.
 
 
Statistical analysis
 
The primary endpoint for this study is the change of HbA1c from baseline to

	
double-blind treatment completion (Week 24). Comparison between treatment and control group is made at a significant level of 0.05 (two-sided). A mixed model for repeated measures is used for main analysis of primary endpoint. Subjects included in the analysis should have baseline measurement of the primary efficacy endpoint and at least one post treatment measurement during double-blind treatment period. The factors of the model include groups, visits, the interaction between groups and visit, sites, and baseline HbA1c value. An unstructured covariance structure is preferred for the primary analysis. The Statistical Analysis Plan prepared separately provides the details for other covariance structures in case the preferred covariance model does not converge. The primary analysis provides point estimation and 95% confidence interval for the difference in the change of HbA1c from baseline between between groups (treatment group-control group).


Population  Pharmacokinetic/  Pharmacodynamic  Analysis (PopPK/PD)
	
The PopPK/PD model for HMS5552 is updated by using the NONMEM/PIRANA/R software based on the current HMS5552 PopPK/PD model and PK/PD data in Chinese subjects with T2DM after HMS5552 treatment. The quantitative relationship between HMS5552 concentration and HbA1c level is established. Systemic quantitative analysis is conducted on the influences of various factors on HMS5552 PK/PD characteristics, e.g., demographics, disease course, concomitant medications, etc.

## Study Flow Chart

## Schedule of Assessments

-	Screening	Run-in Period 		Randomization	Double-Blind Treatment Period						Open-Label Treatment Period					Safety Observation
Visit number	Visit 1	Visit 2	Visit 3	Visit 4	Visit 5	Visit 6	Visit 7	Visit 8	Visit 9	Visit 10 	Visit 11	Visit 12	Visit 13	Visit 14	Visit 15 	Visit 16 
Visit time	Week -6 to -4	Week -4 ± 3 days	Day -5 ± 2 days	Day 1	Week 4 ± 4 days	Week 8 ± 4 days	Week 12 ± 4 days	Week 16 ± 4 days	Week 20 ± 4 days	Week 24 ± 4 days	Week 28 ± 4 days	Week 34 ± 6 days	Week 40 ± 6 days	Week 46 ± 6 days	Week 52 ± 6 days	Week 53 ± 2 days
Study Procedures																
Informed consent	X															
Demographics	X															
Medical history and prior medications	X			X												
Inclusion/exclusion criteria	X			X												
Concomitant medications	X	X	X	X	X	X	X	X	X	X	X	X	X	X	X	X
Randomization				X												
Adverse events		X	X	X	X	X	X	X	X	X	X	X	X	X	X	X
Physical examination 	X			X	X	X	X	X	X	X	X	X	X	X	X	
Vital signs 	X			X	X	X	X	X	X	X	X	X	X	X	X	
12-Lead ECG	X		X	X	X	X	X	X	X	X	X	X	X	X	X	
Laboratory Tests (in central laboratory)																
HbA1c	X		X	X	X	X	X	X	X	X	X	X	X	X	X	
FPG	X		X	X	X	X	X	X	X	X	X	X	X	X	X	
Hematology 	X		X	X	X	X	X	X	X	X	X	X	X	X	X	
Urinalysis 	X		X	X	X	X	X	X	X	X	X	X	X	X	X	
Blood biochemistry 	X		X	X	X	X	X	X	X	X	X	X	X	X	X	
Virology test 	X															
Pregnant test 	X	X	X	X	X	X	X	X	X	X	X	X	X	X	X	
MMTT 				X			X			X						X
Biomarker 	X			X			X			X						X
PK sampling 					X		X			X						X
DNA sample 				X												
Instructions/Suggestions																
Health education 	X	X	X	X	X	X	X	X	X	X	X	X	X	X	X	
Glucometer distribution		X														
SMBG check 			X	X	X	X	X	X	X	X	X	X	X	X	X	
Subject diary		X		X	X	X	X	X	X	X	X	X	X	X	X	
Study Medication																
Drug distribution		X		X	X	X	X	X	X	X	X	X	X	X	X	
Review of drug usage and recycling 				X	X	X	X	X	X	X	X	X	X	X	X	

ECG: electrocardiogram; eCRF: electronic case report form; FPG: fasting plasma glucose; HbA1c: glycosylated hemoglobin; MMTT: mixed-meal tolerance test; SMBG: self-monitoring of blood glucose.

**Note:** a. All laboratory sampling must be completed under fasting before dosing (except for 30 min and 120 min MMTT sampling), suggested time: 7:00 to 10:00 a.m. b. MMTT is suggested to start between 7:00 and 9:00 a.m. c. The schedule of visit window is based on normal working time. In case of the National Day, Spring Festival and other holidays, the Investigator can arrange for administration of the study medications accordingly and reschedule the visit to a time closest to the visit scheduled per study protocol. Causes for early/late visit will be recorded on eCRF but are not considered as protocol deviation.

1. Single-blind placebo run-in period lasts from Day  $-28 \pm 3$  days to Day -1 (inclusive).
2. The double-blind treatment period (Visit 10) ends when subjects complete all the 24-week treatment. If early withdrawal occurs in the double-blind treatment period, a termination visit needs to be conducted for the patient within 7 days (the seventh day included) after the last dose of study medications. In addition, a telephone follow-up for safety is conducted within 1 week after the last dose of study medications. If administration of the study medications has been stopped by the subjects for  $\geq 7$  days before early withdrawal, a termination visit needs to be completed as much as possible. The tests in the termination visit are the same as Visit 15.
3. The open-label treatment period (Visit 15) ends when subjects finish all the 52-week treatment. If early withdrawal occurs in the open-label treatment period, a termination visit needs to be completed within 7 days (the seventh day included) after the last dose of study medications. In addition, a telephone follow-up for safety is conducted within 1 week after the last dose of study medications. If administration of the study medications has been stopped by the subjects for  $\geq 7$  days before early withdrawal, a termination visit needs to be completed as much as possible. The tests in the termination visit are the same as Visit 15.
4. All study medications are stopped in the safety observation period. Visit 16 is conducted by telephone at which adverse events and concomitant medications occurring in the safety observation period are recorded. If there is any adverse event that has occurred during the treatment period and is still ongoing, the investigator should arrange the follow-up visit based on the need of adverse event during the observation period and carry out corresponding examinations.
5. Physical examinations: general appearance, head, neck, chest (heart and lungs), abdomen, and limbs etc.
6. Vital signs: for Visit 1, blood pressure, pulse rate, breath rate, body temperature (axillary), height, weight. For other visits, all parameters except height are checked.
7. Hematology: hemoglobin, hematocrit, erythrocytes count, leukocytes count, neutrophils, basophils, eosinophils, monocytes, lymphocytes, and platelet count.
8. Urinalysis: pH, specific gravity, protein, glucose, erythrocytes, leukocytes, and ketone bodies.
9. Blood biochemistry: blood glucose, total bilirubin, alanine aminotransferase, aspartate aminotransferase, gamma-glutamyl transferase, alkaline phosphatase, albumin, total protein, lactate dehydrogenase, blood urea nitrogen, creatinine, uric acid, sodium, potassium, chloride, calcium, creatine kinase, creatine kinase isoenzyme, total cholesterol, high-density lipoprotein cholesterol, low-density lipoprotein cholesterol, and triglyceride.
10. Virology test: hepatitis A virus IgM antibody, hepatitis B surface antigen (HBsAg), hepatitis B surface antibody (anti-HBs), IgM antibody to hepatitis B core antigen (IgM anti-HBc), hepatitis C virus antibody (anti-HCV), human immunodeficiency virus (HIV) antibody.

11. Pregnancy test (only for females with childbearing potential). From Visit 1 to Visit 15, blood pregnancy test must be performed in the central laboratory. During the study, if any amenorrhea or irregular menstruation is reported for any female subject at any time, a blood pregnancy test should be performed in the central laboratory immediately to exclude or validate pregnancy. Drug administration is stopped immediately once a positive result is shown.
12. MMTT: The blood samples for evaluating plasma glucose, insulin and C-peptide are collected 30 minutes ( $\pm 3$  minutes) and 120 minutes ( $\pm 5$  minutes) after the instant noodles standard meal being taken, which is provided by the Sponsor. The standard meal should be taken before drug administration at Visit 4. At Visits 7, 10 and 15, the standard meal is taken after drug administration (blood sampling at 30 minutes after the standard meal is applicable to subjects enrolled after the protocol v1.1 taking effect).
13. Biomarker: including fasting insulin and C-peptide. At Visit 1, only C-peptide is tested and evaluated as one of the exclusion criteria.
14. Population pharmacokinetics. At Visit 5, blood samples are collected before drug administration. At Visits 7, 10 and 15, blood sampling schedule is the same as 120-minute MMTT. The time of blood sampling and the time (before Visit Day) for the closest drug administration before blood sampling are recorded in detail (not on the same day of visit, usually one day before the visit).
15. DNA sampling: At Visit 4, DNA samples are collected (optional).
16. Diabetes education and health/exercise guidance. The Investigator fully assesses the life and disease status for each subject. If any inappropriate lifestyle is identified (e.g., eating or drinking too much in holidays) for any subject, the diabetes education and health/exercise guidance should be given to him/her timely and repeatedly.
17. SMBG examination. For each subject, fingertip blood glucose under fasting or postprandial is required to be monitored at least twice a week at home. If suspicious hypoglycemia or hyperglycemia events occur, additional blood glucose tests should be conducted and the results are recorded in subject diaries. At each visit, the Investigator should review the subject diaries carefully then make suggestions on drug administration and blood glucose monitoring for next stage.
18. Review of drug usage and recycling: The Investigator should review the drug compliance record from Visit 2 to Visit 4 (run-in period) and from Visit 4 to Visit 15 (treatment period). Queries should be made if any problem is found. At Visit 4, drug compliance is evaluated for the run-in period. Guidance should be given if any subject does not follow the drug administration specified in the study protocol.

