### **3.5.7 Visit 7: Treatment Visit (Day 84 ± 4 days)**

The following procedures are completed at Visit 7 (all laboratory tests are conducted in the central laboratory, blood samples are collected when subjects are in fasting status, except for 30-minute and 120-minute MMTT samples):

- Vital signs (blood pressure, pulse rate, breath rate, body temperature, and body weight);
- Physical examination: general appearance, head and neck, chest (heart and lungs), abdomen, limbs etc.;
- Laboratory tests (samples are suggested to be collected between 7:00 and 10:00 am):

Assessment of diabetes status: HbA1c and FPG;

Hematology: hemoglobin concentration, hematocrit, erythrocytes, leukocytes, neutrophils, basophils, eosinophils, monocytes, lymphocytes, and platelets;

Urinalysis: pH, specific gravity, protein, glucose, erythrocytes, leukocytes, and ketone bodies;

Blood biochemistry: total bilirubin, ALT, AST, gamma-glutamyl transferase, alkaline phosphatase, albumin, total protein, lactate dehydrogenase, urea nitrogen, creatinine, uric acid, sodium, potassium, chloride, calcium, creatine kinase, creatine kinase isoenzyme, total cholesterol, high-density lipoprotein cholesterol, low-density lipoprotein cholesterol, and triglyceride;

- Blood pregnancy test (only applicable to females with childbearing potential);
- MMTT: the test must be conducted after blood sampling for HbA1c and other laboratory tests is completed, and after taking study medications. Refer to

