Appendix 3 for MMTT procedures;

- Blood sampling for population PK (before drug administration, 120-minute MMTT);
- Biomarkers;
- 12-lead ECG;
- SMBG status: review SMBG records and provide instructions on SMBG for next stage;
- Review study medication usage and recycling. Subject diaries are reviewed. The drug administration record is reviewed and confirmed. Instructions are given to subjects who do not take study medications per protocol.
- AEs and concomitant medications;
- A new subject diary is dispensed;
- Diabetes education, instructions on diet and exercise are provided;
- Study medications are dispensed.

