### **6. Study Endpoints**

The methods for assessment and documentation of study endpoints and time for assessment are as follows. The efficacy parameters include HbA1c, PPG and FPG.

Follow up visits are scheduled at Weeks 4, 8, 12, 16, 20, 24, 28, 34, 40, 46, 52 after study treatment starts. Efficacy parameters, e.g. HbA1c and FPG, are tested at each visit (refer to the Flow Chart of Clinical Study for details on assessments). The visit window for Weeks 4, 8, 12, 16, 20, 24 and 28 is defined as  $\pm$  4 days of visiting day; whereas the visit window for Weeks 34, 40, 46, and 52 is defined as  $\pm$  6 days of visiting day; and visit window of  $\pm$  2 days for Week 53 phone visit is suggested. The schedule of visit window is based on normal working time. In case of the National Day, Spring Festival and other holidays, the Investigator can arrange for administration of the study medications accordingly and reschedule the next visit to a time closest to the visit scheduled per study protocol. Causes for early/late visit are recorded on eCRF and this is not considered as a protocol deviation.

Study visits are recommended to be arranged between 7:00 and 10:00 a.m. High calorie and high fat diet is not permitted the day before the study visit. Subjects should stay in fasting status for at least 8 hours from 22: 00 on the previous day until sampling for the visit is completed, without intake of food/drink (water is permitted). If a subject is not prohibited from high calorie and high fat diets or not fasted, the sampling for the subject is suggested to be done in the morning next to the scheduled visit. The Investigator should emphasize the importance of prohibition on high calorie and high fat diets and sampling in fasting status.

The Investigator should inform the subjects not taking study medications in the morning of study visit. The study medications should be taken after sampling in fasting status. Then the MMTT is conducted. The Investigator should also remind subjects of returning the remaining medications on the day of study visit.

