11. Pregnancy test (only for females with childbearing potential). From Visit 1 to Visit 15, blood pregnancy test must be performed in the central laboratory. During the study, if any amenorrhea or irregular menstruation is reported for any female subject at any time, a blood pregnancy test should be performed in the central laboratory immediately to exclude or validate pregnancy. Drug administration is stopped immediately once a positive result is shown.
12. Mixed meal tolerance test. The instant noodles standard meal provided by Sponsor should be taken before drug administration at Visit 4. The blood samples for evaluating plasma glucose, insulin and C-peptide are collected 30 minutes( $\pm 3$  minutes) and 120 minutes( $\pm 5$  minutes) after the standard meal. At Visits 7, 10 and 15, the standard meal is taken after drug administration (30-minute blood sampling point is applicable to subjects enrolled after the protocol v1.1 taking effect).
13. Biomarker: insulin and C-peptide. At Visit 1, only C-peptide is tested and evaluated as one of the exclusion criteria.
14. Population pharmacokinetics. At Visit 5, blood samples are collected before drug administration. At Visits 7, 10 and 15, blood sampling schedule is the same as 120 minute MMTT. The time of blood sampling and the time for the closest drug administration before blood sampling are recorded in detail (not on the same day of visit, usually the day before the visit).
15. DNA test. At Visit 4, DNA samples are collected after informed consent form (ICF) is signed. If subject refuse to sign the ICF at Visit 4, he/she can sign at any time during the study and DNA samples are collected after the ICF is signed.
16. Diabetes education and health/exercise guidance. The Investigator fully assesses the life and disease status for each subject. If any inappropriate lifestyle is identified (e.g. eating or drinking too much in holidays) for any subject, the diabetes education and health/exercise guidance should be given to him/her timely and repeatedly.

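### For the 120-minute PK sample at Visits 7, 10 and 15, note 14 asks for a previous-day dose time although a dose is taken on site that morning; followed literally, time after dose could be overstated by roughly 12 hours

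*Supplement*

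**What the plan says.** **Which samples are drawn.** Protocol v1.1, Schedule of Assessments, note 14: "At Visits 7, 10 and 15, blood sampling schedule is the same as 120-minute MMTT". The visit sections go further. Section 3.5.7 lists "Blood sampling for population PK (before drug administration, 120-minute MMTT", which is two samples, and sections 3.5.10 and 3.5.15 list the same two. At Visit 5 (section 3.5.5) there is one sample, before dosing.

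**Which dose time is recorded.** Note 14 goes on: "the time (before Visit Day) for the closest drug administration before blood sampling are recorded in detail (not on the same day of visit". Its closing bracket in full limits the recorded dose to one "not on the same day of visit, usually one day before the visit". SAP 2.3.2, note 14, has the same limit: "not on the same day of visit, usually the day before the visit".

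**Order of events on the visit day.** Note 12 of the schedule: "At Visits 7, 10 and 15, the standard meal is taken after drug administration". Section 3.5.7 allows the meal test only once sampling for HbA1c and other "laboratory tests is completed, and after taking study medications". Section 6 gives the sequence in general terms: "The study medications should be taken after sampling in fasting status. Then the MMTT is conducted". Appendix 3 counts the 120 minutes from the first mouthful of the test meal, with a tolerance of 5 minutes either way.

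**Use of the data.** Section 10 plans an updated PopPK/PD model linking drug concentration to HbA1c. It leaves the methods to a separate analysis plan, as does SAP 9.4. That plan is not among the documents.

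**The concern.** A concentration is only informative in a PK model together with the time since the dose that produced it. At Visits 7, 10 and 15 the 120-minute sample follows a tablet taken an hour or two earlier on the same morning. Note 14 asks for the closest dose before sampling and in the same sentence excludes any dose on the visit day. For this sample both conditions cannot be met.

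If sites enter the previous evening's dose and the analysis takes that entry as the last dose, a concentration that includes the morning tablet would be read as what is left of the evening one. The 120-minute samples are the only PK samples scheduled shortly after a dose, so the error would fall on the samples that tell the model most about the early part of the curve. Exposure estimates feeding the concentration-HbA1c relationship could be distorted.

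**Working it through.** The documents state no figure for time after dose, so there is nothing to reproduce. The check sets the rule against each sample and then works out the size by clock arithmetic.

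**Step 1: does the rule fit each sample?**

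| PK sample | Last dose before it | Does a previous-day dose time fit? |
|---|---|---|
| Visit 5, pre-dose | day before | yes |
| Visits 7, 10, 15, pre-dose | day before | yes |
| Visits 7, 10, 15, at 120 minutes | that morning, on site | no |

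If all samples in the visit sections are drawn, a subject randomised to active drug gives 1 + 3 × 2 = 7 PK samples. Four are covered correctly by the rule and three are not. Note 14 read alone is worse: for Visits 7, 10 and 15 it names only the 120-minute sample, the one its dose rule does not fit.

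**Step 2: true time after dose at 120 minutes.**

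True time = 2 h + lag from dose to start of meal. The documents give no lag. Assuming 0 to 30 minutes, true time = 2.0 to 2.5 h.

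**Step 3: time after dose if the previous evening's dose is used.**

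Apparent time = true time + interval from evening dose to morning dose. The overstatement is that interval. Section 5.1.3 places doses before breakfast and before supper, without clock times, so the interval has to be assumed:

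- Evenly spaced twice-daily dosing: 12 h. Apparent time = 14.0 to 14.5 h.
- Supper dose at 17:00 to 20:00 and morning dose at 7:00 to 9:00 (the schedule suggests starting the meal test in that morning window): shortest interval 24 − 20 + 7 = 11 h, longest 24 − 17 + 9 = 16 h. Apparent time = 2.0 + 11 = 13 h up to 2.5 + 16 = 18.5 h.
- Evening dose as late as 22:00, when section 6 has the fast begin, and morning dose at 7:00: 24 − 22 + 7 = 9 h.

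The overstatement is therefore roughly 12 h, with a range of about 9 to 16 h. For the pre-dose samples it is 0 h.

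**Step 4: who is affected.** At Visits 7 and 10 only subjects on active drug matter: 450 × 2/3 = 300 at the planned size, and at most 376 at the enrolment ceiling. At Visit 15 all remaining subjects are on active drug.

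**Step 5: is the on-site dose time required elsewhere?** Diaries cover daily drug use (section 3.6), without a stated requirement for clock times. Section 7.13 mentions a dosing page in the eCRF, in connection with overdose. No section shown expressly requires the clock time of the visit-day dose. The time of blood sampling is already required by note 14.

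**The case against.** The best defence is that note 14 is about the dose nobody at the site sees. Subjects take a tablet at home the day before and hold the morning one until the visit. The home dose time is what every pre-dose sample needs, and the note does not forbid writing down the on-site dose as well. That dose falls in a fixed sequence of fasting samples, tablet, then meal. A modeller who knows the sequence could insert a nominal morning dose about 2 h before the draw, leaving an error no larger than the unrecorded dose-to-meal lag. The SAP (section 1) cites an eCRF dated June 2019, later than protocol v1.1, and its fields are not shown. The PopPK/PD plan is not shown either.

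This stands as far as it goes. A reader might infer that time after dose will be wrong in the model. The documents do not show that, because the on-site time may be captured in the eCRF, a diary or site records, or handled in the PopPK/PD plan. A reader might also turn 12 h into a fold-error in predicted concentration. The documents give no half-life and no time to peak, so any such factor would rest on assumed pharmacokinetics. Nor has any bias in clearance or exposure been calculated, and the planned analysis updates an existing model with correctly timed pre-dose samples also available.

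What the defence does not remove is the wording. For the 120-minute sample the rule names the wrong dose, in both current documents, and an analysis plan cannot recover an exact time that was never collected.

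**Conclusion.** The point holds as an internal contradiction in a data-recording rule. The previous-day dose time is right for the pre-dose samples at Visits 5, 7, 10 and 15, and wrong for the 120-minute sample at Visits 7, 10 and 15. Because the note gives a positive instruction that yields a wrong input if obeyed, this is more than missing detail.

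The size is conditional on two things: that sites follow the note literally, and that no other record supplies the on-site dose time. Under those conditions time after dose could be overstated by roughly 12 h, or about 9 to 16 h under the assumed dosing times. The harm is confined to the PopPK/PD modelling, which is not among the listed objectives or endpoints. The primary HbA1c comparison and the secondary efficacy and safety analyses do not use these times.

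**What to change.** - Reconcile note 14 of the protocol schedule and note 14 of SAP 2.3.2 with sections 3.5.7, 3.5.10 and 3.5.15 on which PK samples are drawn at Visits 7, 10 and 15 (pre-dose and 120-minute).
- Keep the previous-day dose time for the pre-dose samples.
- Require the clock time of the visit-day dose for the 120-minute sample at Visits 7, 10 and 15.
- Check that the eCRF has a field for that time, and add one if it does not.

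The cost is about one sentence in each document and, at most, one eCRF time field. No blood draw is added and dosing does not change. The change has to reach sites before the visits take place, since a dose time not noted on the day may not be recoverable later.
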